Appendix 3 Contraception and Barrier Requirements

Definitions:

Women of Child-Bearing Potential:

A woman is of childbearing potential (fertile) following menarche and until becoming postmenopausal unless permanently sterile, as specified below.

If fertility is unclear (e.g., amenorrhea in adolescents or athletes) and a menstrual cycle cannot be confirmed before the first dose of study intervention, consider additional evaluation.

Postmenopause:

Postmenopause is defined as no menses for 12 months without an alternative medical cause.

- A high FSH level in the postmenopausal range may be used to confirm a postmenopausal state in a female not using hormonal contraception or HRT. However, in the absence of 12 months of amenorrhea, confirmation with more than 1 FSH measurement (> 40 mIU/mL) is required.
- A female on HRT and whose menopausal status are in doubt will be required to use 1 of the nonestrogen hormonal highly effective contraception methods if she wishes to continue her HRT during the study. Otherwise, she must discontinue HRT to allow confirmation of postmenopausal status before study enrollment.

Permanent sterilization:

For this study, permanent sterilization includes:

- Documented hysterectomy
- Documented bilateral salpingectomy
- Documented bilateral oophorectomy

Documentation can come from the site personnel's review of the individual's medical records, medical examination, or medical history interview.

For individuals with permanent infertility due to an alternate medical cause other than the above, (e.g., Mullerian agenesis, androgen insensitivity), Investigator discretion applies to determine study entry.

Contraception Guidance:

CONTRACEPTIVES ALLOWED DURING THE STUDY INCLUDE:

Highly Effective Methods That Have Low User Dependency
 
• Implantable progestogen-only hormone contraception associated with inhibition of ovulation• IUD• IUS• Bilateral tubal occlusion• Vasectomized partner: a highly effective contraceptive method provided that the partner is the sole sexual partner of a WOCBP, and the absence of sperm has been confirmed. Otherwise, use an additional highly effective method of contraception. The spermatogenesis cycle is approximately 90 days.

Highly Effective Methods That Are User Dependent
 
• Combined (estrogen- and progestogen-containing) hormonal contraception associated with inhibition of ovulation
• Oral• Intravaginal• Transdermal• Injectable• Progestogen-only hormone contraception associated with inhibition of ovulation
• Oral• Injectable• Sexual abstinence: a highly effective method only if defined as refraining from intercourse during the entire period of risk associated with the study intervention. The reliability of sexual abstinence needs to be evaluated in relation to the duration of the study and the preferred and usual lifestyle of the participant.

Notes:
 
Contraceptive use by men or women is consistent with local regulations on the use of contraceptive methods for clinical study participants.
 
Highly effective methods are those with a failure rate of < 1% per year when used consistently and correctly. Typical use failure rates differ from those when used consistently and correctly.
 
If locally required, in accordance with CTFG guidelines, acceptable contraceptive methods are limited to those which inhibit ovulation as the primary mode of action.
 
Periodic abstinence (calendar, symptothermal, postovulation methods), withdrawal (coitus interruptus), spermicides only, and lactation amenorrhea method are not acceptable methods of contraception for this study. Male condom and female condom cannot be used together (due to risk of failure from friction).

Appendix 4 Adverse Events: Definitions and Procedures for Recording, Evaluating, Follow-up, and Reporting

AE Definition

- An AE is any untoward medical occurrence in a patient or clinical study participant, temporally associated with the use of study intervention, whether considered related to the study intervention or not.
- An AE can therefore be any unfavorable and unintended sign (including an abnormal laboratory finding), symptom, or disease (new or exacerbated) temporally associated with the use of study intervention. For surgical or diagnostic procedures, the condition/illness leading to such a procedure is considered as the AE rather than the procedure itself.

Events Meeting the AE Definition

- Any abnormal laboratory test results (hematology, clinical chemistry, or urinalysis) or other safety assessments (e.g., ECG, radiological scans, vital signs measurements), including those that worsen from baseline and are judged to be more severe than expected for the participant's condition are considered clinically significant in the medical and scientific judgment of the Investigator (i.e., not related to progression of underlying disease, but may be leading to study intervention discontinuation).
- Exacerbation of a chronic or intermittent preexisting condition including either an increase in frequency and/or intensity of the condition.
- New conditions detected or diagnosed after study intervention administration even though it may have been present before the start of the study.
- Signs, symptoms, or the clinical sequelae of a suspected drug-drug interaction.
- Signs, symptoms, or the clinical sequelae of a suspected overdose of either study intervention or a concomitant medication.
- “Lack of efficacy” or “failure of expected pharmacological action” per se will not be reported as an AE or a SAE. However, the signs, symptoms, and/or clinical sequelae resulting from lack of efficacy will be reported as an AE or a SAE if they fulfil the definition of an AE or SAE.

Events NOT Meeting the AE Definition

- Unless judged by the Investigator to be more severe than expected for the participant's condition, any clinically significant abnormal laboratory findings, other abnormal safety assessments that are associated with the underlying disease, the disease/disorder being studied within the expectedness for participant's condition, as judged by the Investigator.
- Medical or surgical procedure (e.g., endoscopy, appendectomy): the condition that leads to the procedure is the AE.
- Situations in which an untoward medical occurrence did not occur (social and/or convenience admission to a hospital).

- Anticipated day-to-day fluctuations of preexisting disease(s) or condition(s) present or detected at the start of the study that do not worsen.

SAE Definition

If an event is not an AE per the definition above, then it cannot be an SAE even if serious conditions are met (e.g., hospitalization for signs/symptoms of the disease under study, death due to progression of disease).

A SAE is defined as any untoward medical occurrence that, at any dose:

a. Results in death

b. Is life-threatening

The term 'life-threatening' in the definition of 'serious' refers to an event in which the participant was at risk of death at the time of the event. It does not refer to an event, which hypothetically might have caused death, if it were more severe.

c. Requires inpatient hospitalization or prolongation of existing hospitalization

- In general, hospitalization signifies that the participant has been detained (usually involving at least an overnight stay) at the hospital or emergency ward for observation and/or treatment that would not have been appropriate in the physician's office or outpatient setting. Complications that occur during hospitalization are AEs. If a complication prolongs hospitalization or fulfils any other serious criteria, the event is serious. When in doubt as to whether "hospitalization" occurred or was necessary, the AE will be considered serious.
- Hospitalization for elective treatment of a preexisting condition that did not worsen from baseline is not considered an AE.
- However, all events leading to unplanned hospitalizations or unplanned prolongation of an elective hospitalization must be documented and reported as SAEs.

d. Results in persistent disability/incapacity

The term disability means a substantial disruption of a person's ability to conduct normal life functions.

This definition is **not** intended to include experiences of relatively minor medical significance such as uncomplicated headache, nausea, vomiting, diarrhea, influenza, and accidental trauma (e.g., sprained ankle) which may interfere with or prevent everyday life functions but do not constitute a substantial disruption.

e. Is a congenital anomaly/birth defect

f. Other situations:

- Medical or scientific judgment will be exercised in deciding whether SAE reporting is appropriate in other situations, such as important medical events that may not be immediately life-threatening or result in death or hospitalization but may jeopardize the participant or may require medical or surgical intervention to prevent 1 of the other outcomes listed in the above definition. These events are usually considered as serious.
- Examples of such events include invasive or malignant cancers, intensive treatment in an emergency room or at home for allergic bronchospasm, blood dyscrasias or convulsions that do not result in hospitalization, or development of drug dependency or drug abuse.

Any suspected transmission of an infectious agent via a study intervention is also considered an SAE for reporting purposes, as specified below for reporting SAEs or AESIs.

Recording and Follow-Up of AE and/or SAE

AE and SAE Recording

- When an AE/SAE occurs, it is the responsibility of the Investigator to review all documentation (e.g., hospital progress notes, laboratory reports, and diagnostics reports) related to the event.
- The Investigator will then record all relevant AE/SAE information in the CRF.
- As needed, the Sponsor/designee may ask for copies of certain medical records (e.g., autopsy reports, supplemental lab reports, documents on medical history/concomitant medications, discharge letters), as supporting source documentation. All participant identifiers, except the participant number, will be redacted on these copies before submission to the Sponsor/designee.
- The Investigator will attempt to establish a diagnosis of the event based on signs, symptoms, and/or other clinical information. Whenever possible, the diagnosis (not the individual signs/symptoms) will be documented as the AE/SAE.
- Specific guidance is in the CRF Completion and Monitoring Conventions.

Assessment of Intensity

The Investigator will assess the intensity of each AE and SAE reported during the study and assign it to 1 of the following categories:

- Mild: An event that is easily tolerated by the participant, causing minimal discomfort and not interfering with everyday activities.
- Moderate: An event that causes sufficient discomfort and interferes with normal everyday activities.

- Severe: An event that prevents normal everyday activities. Do not confuse an AE that is assessed as severe with a SAE. Severe is a category used to rate the intensity of an event; both AEs and SAEs can be assessed as severe.

An event is defined as “serious” when it meets at least 1 of the predefined criteria specified in the definition of an SAE, NOT when it is rated as severe.

Assessment of Causality

- The Investigator will assess the relationship between study intervention and each AE/SAE occurrence:
 - Unrelated: Not reasonably related to the study intervention. AE could not medically (pharmacologically/clinically) be attributed to the study intervention. A reasonable alternative explanation will be available.
 - Related: Reasonably related to the study intervention. AE could medically (pharmacologically/clinically) be attributed to the study intervention.
 - A “reasonable possibility” of a relationship conveys that there are facts, evidence, and/or arguments to suggest a causal relationship, rather than a relationship cannot be ruled out.
- The Investigator will use clinical judgment to determine the relationship.
- Alternative causes, such as underlying disease(s), concomitant therapy, and other risk factors, as well as the temporal relationship of the event to study intervention administration will be considered and investigated.
- The Investigator will also consult the IB and/or Product Information, for marketed products, in his/her assessment.
- For each AE/SAE, the Investigator will document in the medical notes that he/she has reviewed the AE/SAE and assessed causality.
- There may be situations when an SAE has occurred, and the Investigator has minimal information to include in the initial report to the Sponsor or its designee. To meet the reporting timeline, the causality assessment is not required for the initial report.
- The Investigator may change his/her causality assessment after considering follow-up information and send a SAE follow-up report with the updated causality assessment.
- The causality assessment is 1 of the criteria used when determining regulatory reporting requirements.

Follow-up of AEs and SAEs

- The Investigator will perform or arrange for the conduct of supplemental measurements and/or evaluations, as medically indicated or as requested by the Sponsor/designee to elucidate the nature and/or causality of the AE or SAE, as fully as possible. This may include additional laboratory tests or investigations, histopathological examinations, or consultation with other health care professionals.
- If a participant dies during participation in the study or during a recognized follow-up period, the Investigator will provide the Sponsor/designee with a copy of any postmortem findings including histopathology.
- New or updated information will be recorded in the originally completed CRF.
- The Investigator will submit any updated SAE data to the Sponsor/designee within 24 hours of receipt of the information.

Reporting of SAEs

SAE Reporting by a Paper Form

- SAE reporting on a paper report form may be used in single center studies in addition to the standard electronic CRF and as a back-up method for an EDC system failure. The form includes completion instructions for the Investigator, names, addresses, and telephone and fax numbers. All information from the paper form will be transcribed into the electronic form as soon as the system becomes available.
- Facsimile transmission (fax to mail) of the paper form or any follow-up information is the preferred method for transmission and will be done within 24 hours to the Sponsor or its designee.
- In rare circumstances and in the absence of facsimile equipment, notification by telephone is acceptable with a copy of the form sent by overnight mail or courier service.
- Initial notification via telephone does not replace the need for the Investigator to complete and sign the form within 24 hours after becoming aware of the event.
- Additional documents (e.g., laboratory reports, autopsy report, hospital discharge letter) and relevant pages from the CRF may be required in addition (e.g., medical history, concomitant medication). The data provided will be consistent with the information in the CRF.

Reporting of AESIs

- For a nonserious AESI, the site will complete the specific AESI report form and notify the Sponsor immediately (within 24 hours), using the same process for reporting SAEs, as specified above.
- For a serious AESI, the site will complete an SAE report form, using the SAE reporting process, specified above.

Reporting of Pregnancies

- Pregnancy will be reported whether related to the study intervention using the applicable paper form.
- The applicable form will be used to report if an abnormal outcome of the pregnancy occurs and the child/fetus sustains an event.
- Facsimile transmission (fax to mail) of the paper form or any follow-up information is the preferred method for transmission and will be done within 24 hours to the Sponsor or its designee.

Appendix 5 Clinical Laboratory Tests

The protocol-required clinical laboratory assessments are in the following table:

Laboratory Assessments	Parameters				
Hematology	Platelet count		Mean corpuscular volume (MCV)	White Blood Cell Count with Differential: Neutrophils Lymphocytes Monocytes Eosinophils Basophils	
	Hemoglobin		Mean corpuscular hemoglobin (MCH)		
	Hematocrit				
Biochemistry	Blood Urea Nitrogen	Potassium	Aspartate aminotransferase	Bilirubin	
	Creatinine	Sodium	Alanine aminotransferase	Protein	
	Glucose	Calcium	Alkaline phosphatase	Albumin	
	Uric acid	Chloride	γ -Glutamyl transferase	Cholesterol	
		Inorganic phosphate	Lactate dehydrogenase	Triglycerides	
		Magnesium	Creatinine phosphokinase	Amylase	
				Lipase	
Routine Urinalysis	
 Specific gravity pH, glucose, protein, blood (hemoglobin), ketones, bilirubin, urobilinogen, nitrite, leukocyte esterase by dipstick Microscopic examination (if blood or protein is abnormal). Note: In case of a positive result for hemoglobin, leukocyte esterase, protein or nitrite, a urinary cell count will be performed				
Coagulation	
 INR aPTT 				
Other Screening Tests	
 FSH Serum hCG pregnancy test (as needed for a WOCBP) at all timepoints listed in the Schedule of Assessments (Section 1.3) Urine drug screen (to include at minimum: amphetamines, methamphetamines, barbiturates, ecstasy, cocaine, opiates, cannabinoids, benzodiazepines, methadone, phencyclidine, oxycodone, and tricyclic antidepressants, Screening and Day -1 / Day 11) Serology (human immunodeficiency virus I and II antibodies, hepatitis B surface antigen, hepatitis B core antibody, hepatitis C antibody) SARS-CoV-2 rapid antigen test at Screening, PCR test at admission on Day -1 Thyroid stimulating hormone Cotinine test (Screening and Day -1 / Day 11) Alcohol breath test (Screening and Day -1 / Day 11) Estimated Glomerular Filtration Rate based on Chronic Kidney Disease Epidemiology Collaboration Creatinine Equation (2009) All study-required laboratory assessments will be performed by a central laboratory (Nuvisan's clinical laboratory) 				

aPTT=activated partial thromboplastin time, FSH=follicle stimulating hormone, hCG=human chorionic gonadotropin, INR=International Normalized Ratio, PCR=polymerase chain reaction, SARS-CoV-2=severe acute respiratory syndrome coronavirus 2, WOCBP=woman of child-bearing potential.

CCI

Page 10

11

1000

1

10 of 10

Page 10

10 of 10

100

1

1000

1000

111

[REDACTED]

1

Page 10

1

1000

CONFIDENTIAL
INFORMATION

66/68

Global Version ID: CCI

The purpose of this IAP is to document technical and detailed specifications for the final analysis of data collected for protocol MS200095_0053. Results of the analyses described in this IAP will be included in the CSR. Additionally, the planned analyses identified in this IAP may be included in regulatory submissions or future manuscripts. Any post-hoc, or unplanned analyses performed to provide results for inclusion in the CSR but not identified in this prospective IAP will be clearly identified in the CSR.

The IAP is based upon Section 9 (Statistical considerations) of the study protocol and protocol amendments and is prepared in compliance with ICH E9. It describes analyses planned in the protocol and protocol amendments.

The wording used in this IAP is chosen to best match the respective wording in the study protocol template, the Clinical Study Report (CSR) template, CDISC requirements and special requirements for table layouts. Therefore, the following approach is used:

Generally, the term ‘participant’ will be used instead of ‘subject’ or ‘patient’. However, in tables and listings the term ‘subject’ will be used to match CDISC requirements, except for in-text tables where ‘participant’ will be used to match the CSR and protocol templates. Similarly, the term ‘study intervention’ will be used in this document instead of ‘treatment’ to match protocol and CSR templates, however, tables and listings will use ‘treatment’ for brevity reasons. Exceptions from this rule are commonly used terms like “on-treatment”, “treatment-emergent”, “treatment policy”, “subject-years”, “by-subject”, or names of eCRF pages like “Treatment Termination” page.

5 Objectives and Endpoints

Objectives	Endpoints	Ref #
Primary		
To investigate the effect of multiple doses of itraconazole on tepotinib PK in healthy participants	Plasma tepotinib: AUC _{0-∞} , AUC _{0-t_{last}} and C _{max}	1
Secondary		
To assess the safety and tolerability of tepotinib when administered together with itraconazole in healthy participants	
• Nature, occurrence, severity, and seriousness of TEAEs• Absolute values and changes in safety laboratory tests• Single 12-lead ECGs evaluated by Investigator• Vital signs assessed from time of first dose to end of study participation	2
To characterize the effect of multiple doses of itraconazole on additional tepotinib PK parameters in healthy participants	Plasma tepotinib: CL/F, Vz/F, t _{max} , t _{1/2}	3
CCI [REDACTED]	[REDACTED]	[REDACTED]
[REDACTED]	[REDACTED]	[REDACTED]
[REDACTED]	[REDACTED]	[REDACTED]
[REDACTED]	CCI [REDACTED]	[REDACTED]

ECG=electrocardiogram, CCI [REDACTED], PK=pharmacokinetics, TEAE=treatment emergent adverse events.

6 Overview of Planned Analyses

The final, planned analyses identified in the CSP and in this IAP will be performed after the last participant has completed the last visit and after all data queries resolved as well as the database locked.

A data review meeting will be held prior to database lock for the final analysis. In addition, no database can be locked until this IAP has been approved.

7 Changes to the Planned Analyses in the Clinical Study Protocol

There are no changes to the planned analyses in the clinical study protocol.

8 Analysis Sets and Subgroups

8.1 Definition of Analysis Sets

Analysis Set	Description
Screening (SCR)	All participants, who provided informed consent, regardless of the participant's enrollment and study intervention status in the study.
Safety (SAF)	All participants, who were administered any dose of any study intervention. Analyses will consider participants as treated.
Pharmacokinetic (PK)	The PK Analysis Set is a subset of the SAF, and the PK population will include all participants: Who have completed the study without any relevant protocol deviations and factors likely to affect the comparability of PK results. With adequate study intervention compliance. With evaluable PK data, i.e., non-missing values for primary endpoints. If participants received prohibited concomitant therapy or medicines, as specified in Section 6.8.3 of the CSP, they will be excluded from the PK population. All PK analyses will be based on this analysis set.

8.2 Subgroup Definition and Parameterization

Not applicable.

9 General Specifications for Data Analyses

The results of this study will be reported using summary tables, figures, and data listings, as appropriate. All data will be summarized by study intervention and/or scheduled time point, as applicable.

Listings

In the individual participant data listing all individual data will be listed as measured. Repeated and unscheduled measurements will be included in the listings. All listings will be sorted by subject ID, study intervention, and nominal time point, as appropriate.

Tables and Descriptive Statistics

All data will be summarized by study intervention and nominal time point, as appropriate. Repeated and unscheduled measurements included in the listings will not be used for statistical analyses or summaries, unless the repeated measurement was performed due to unreliable values/technical reasons, e.g., clotted samples.

Unless otherwise specified, continuous variables will be summarized using descriptive statistics, i.e. the number of participants with non-missing values (n), the number of participants with missing values, (nmiss), mean, standard deviation, median, 25th percentile (Q1) and 75th percentile (Q3), minimum, and maximum. If there are no missing values the number of participants with missing values should be indicated by a 0. Mean, Median, Q1, Q3, Min, Max will have the same precision

as the SDTM data (decimal places). SD will be presented with one decimal place more than the mean.

Qualitative variables will be summarized by frequency counts and percentages. Unless otherwise stated the calculation of proportions will be based on the number of participants of the analysis set of interest that received the respective study intervention for AE and PK tables and for all other evaluations the analysis set of interest [N]. Therefore, counts of missing observations will be included in the denominator and presented as a separate category.

Study day 1 for this study is defined as the start date of study intervention.

The following labels will be used for the study interventions in tables and listings, if not stated otherwise:

Tepotinib:	Tepotinib: 500 mg on Day 1
Itraconazole:	Itraconazole: 200 mg on Days 8-11
Itraconazole+Tepotinib:	Itraconazole: 200 mg on Days 12-18 plus Tepotinib: 500 mg on Day 12

All statistical analyses will be performed using SAS® Software version 9.4 or higher.

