9.2 Sample Size Determination

A maximum of 18 participants will be assigned to study interventions such that at least 14 evaluable participants complete the study.

Although no hypothesis tests will be performed, the sample size of the study should be sufficient to estimate the difference between dosing conditions with adequate precision.

Available information on intraparticipant variability of tepotinib PK parameters following administration of TF2 and/or TF3 under different dosing conditions, observed in studies MS200095_0044, MS200095_0038 and MS200095_0039 are presented in [Table 3](#). The intraparticipant CV is approximately between 10.4% and 18.0% for $AUC_{0-\infty}$ and $AUC_{0-t_{last}}$, and for C_{max} between 12.7% and 16.4%.

Table 3 Overview of Observed Intraparticipant Variability of Tepotinib Pharmacokinetic Parameters

Study	Comparison	N	Mixed Intraparticipant CV		
			$AUC_{0-t_{last}}$	$AUC_{0-\infty}$	C_{max}
MS200095_0044 Part A	TF3 versus TF2 (fasted)	38	15.77%	15.83%	13.94%
MS200095_0044 Part B	TF2 (fed versus fasted)	14	17.96%	17.95%	12.67%
MS200095_0044 Part C	TF3 (fed versus fasted)	12	14.93%	15.10%	16.79%
MS200095_0038	5 × 100 mg TF3 versus 2 × 250 mg TF3 (fasted)	18	15.26%	15.29%	16.37%
MS200095_0039	Tepotinib Fed + Omeprazole versus Tepotinib Fed	12	10.41%	10.93%	16.22%

CV=Coefficient of Variation, N=number of participants.

Thus, assuming an intraparticipant CV (%) of 10%, 15%, and 20% for AUC and C_{max} of tepotinib, the precision for the estimated ratio (coadministration of tepotinib and itraconazole versus tepotinib alone) to be achieved with a given number of evaluable participants is summarized in [Table 4](#). Assuming a CV of 20%, if 14 evaluable participants are included in the study and the observed ratio is exactly 1.0, then the 90% CI for the ratio will be contained with 80% probability in 0.805 to 1.242. If the observed ratio is exactly 2.0, then the corresponding limits are 1.611 to 2.484.

This precision is considered adequate to characterize the effect of multiple doses of itraconazole on the PK of tepotinib. A further increase in sample size does not substantially improve the precision. On the other hand, even with a slightly smaller number of completed participants, the precision will be markedly decreased.

Table 4 Width of the 90% CI for the Ratio of Pharmacokinetic Parameters, for Different Geometric Mean Ratios, Sample Sizes, and Within-Participant CVs

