11.3 Other Baseline Characteristics

Other baseline measurements, such as virus screen, alcohol and drugs of abuse screen, pregnancy test in women, nicotine and alcohol consumption, will be listed.

Baseline characteristics with respect to vital signs, physical examinations, and hematology/biochemistry will be part of Section 15 (Safety Analysis).

12 Previous or Concomitant Therapies/Procedures

Medications will be presented for the SAF.

Previous medications are defined as any medication discontinued prior to the administration of first study intervention. Concomitant medications are defined as any medication taken during the course of the study, with a starting date greater than or equal to the administration of first study intervention, or with a starting date prior to the administration of first study intervention and ongoing at the time of the first administration of study intervention.

The World Health Organization Drug dictionary (WHO-DD), most current version at time of database lock, will be used for coding of prior and concomitant medications and they will be described using Preferred Term (PT) as applicable.

Previous and concomitant medications will be listed. Concomitant procedures, if any, will also be listed.

13 Study Intervention: Compliance and Exposure

The dosing of each participant is monitored by the study nurse or investigator. A listing of date and time of each drug administration and each blood sampling, including time deviations as well as measured plasma concentrations, will be provided sorted by participant. Information on meal intake will be listed by participant, if provided.

14 Efficacy Analyses

Not applicable.

15 Safety Analyses

This section includes specifications for summarizing safety endpoints that are common across clinical studies such as adverse events, laboratory tests and vital signs.

All safety analyses will be performed for the Safety Analysis Set and will be presented by study intervention and nominal timepoint, as appropriate.

Safety analyses will be done according to the as-treated principle.

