15.5 Other Safety or Tolerability Evaluations

Safety ECG data will be summarized by study intervention and time point using descriptive statistics for baseline (see definition in Section 9), each evaluation during the study, and change from baseline to each evaluation. Listing of safety ECG data will be provided.

ECG summaries will include all ECG assessments from screening on. All ECG assessments will be listed.

The analysis of QT data is complicated by the fact that the QT interval is highly correlated with heart rate. Because of this correlation, formulas are routinely used to obtain a corrected value, denoted QTc, which is independent of heart rate. This QTc interval is intended to represent the QT interval at a standardized heart rate. Several correction formulas have been proposed in the literature. The QT interval will be corrected for heart rate by the Fridericia's formula, QTcF, is defined as

$$QTcF = \frac{QT}{\sqrt[3]{RR}} ,$$

where RR represents the RR interval of the ECG, in seconds, and can be estimated as 60/Heart Rate.

Investigator reported interpretation results will also be tabulated by study intervention and time point using the number and percentage of participants for each interpretation category (Normal, Abnormal Not Clinically Significant [NCS], Abnormal Clinically Significant [CS]).

16 Analyses of Other Endpoints/Estimands

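### The ECG interpretation table divides by the whole Safety set, so participants who never received an intervention count in that intervention's denominator

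*SAP*

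**What the plan says.** SAP Section 9 opens its rule for percentages with a default: "Unless otherwise stated the calculation of proportions will be based on the number of participants of the analysis set of interest". It then splits the base in two. The denominator is participants "that received the respective study intervention for AE and PK tables and for all other evaluations the analysis set of interest [N"]. The next sentence adds that "counts of missing observations will be included in the denominator and presented as a separate category".

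For safety, the analysis set is fixed in SAP Section 15: "All safety analyses will be performed for the Safety Analysis Set and will be presented by study intervention and nominal timepoint, as appropriate". SAP 8.1 defines that set as "All participants, who were administered any dose of any study intervention", so one tepotinib tablet intake on Day 1 is enough to be in N for the rest of the study.

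SAP 15.5 states: "Investigator reported interpretation results will also be tabulated by study intervention and time point using the number and percentage of participants" in each category (normal, abnormal not clinically significant, abnormal clinically significant). It names no denominator. The combination column is labelled in SAP Section 9 as "Itraconazole: 200 mg on Days 12-18 plus Tepotinib: 500 mg on Day 12"; the Itraconazole column covers Days 8 to 11.

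On numbers, Protocol 9.2 says: "A maximum of 18 participants will be assigned to study interventions such that at least 14 evaluable participants complete the study".

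**The concern.** The design has one fixed sequence: tepotinib alone, then itraconazole alone, then both. Losses can only accumulate forward. The tepotinib column is essentially complete, because entry to the Safety set normally means having taken tepotinib on Day 1. The two later columns lose people, yet under the default they keep the full N. Someone who left on Day 5 is then counted, as missing, in two interventions they never took.

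Investigator-evaluated ECGs are a listed secondary endpoint for the safety of tepotinib given with itraconazole. Any distortion from this rule is downward and falls on the later columns, including the combination, which is the exposure named in that objective. One report could also show combination AEs out of one number and combination ECG categories out of a larger one. Finally, the missing category would mix two different groups: people who never received the intervention, and recipients whose ECG was not obtained.

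**Working it through.** The plan gives no figure for this, so there is nothing to reproduce. The check has two parts: which rule governs the table, and what that rule does to the percentages.

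**Which rule governs**

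- The ECG interpretation is neither an AE nor a PK table, so it falls under all other evaluations in SAP Section 9.
- SAP 15.5 states no base of its own, so the exception for a rule stated elsewhere is not triggered.
- The as-treated principle (SAP 8.1 and Section 15) says under which intervention a participant's data are shown. It does not say who is in the denominator.
- SAP 9.4 keeps withdrawn participants in analyses up to discontinuation. It points towards a recipient base but sets no denominator either.

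The explicit sentence in SAP Section 9 therefore governs, and the base is the Safety set.

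**Which tables are affected**

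- Disposition (SAP 10.1) uses treated participants, which is the same group as the Safety set.
- Demographics (SAP 11.1) are summarised overall.
- Laboratory values and vital signs (SAP 15.3, 15.4) are summarised as continuous data on non-missing n, and listed.

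That leaves the ECG interpretation as the by-intervention percentage table.

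**Size**

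Inputs: N = 18 in the Safety set (the planned maximum, assuming all are dosed on Day 1), and m = number who receive the combination on Day 12. The range m = 14 to 18 is an assumption taken from the planned minimum of 14 evaluable completers and the maximum of 18.

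With x participants in a category, the displayed percentage is x/N and the rate among recipients is x/m. The ratio of the two is (x/N)/(x/m) = m/N. The share shown as missing only because the combination was never given is (N - m)/N.

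| m | m/18 | Never dosed, shown as missing | x = 1: displayed / recipients | x = 3: displayed / recipients |
|---|---|---|---|---|
| 18 | 1.000 | 0% | 5.6% / 5.6% | 16.7% / 16.7% |
| 17 | 0.944 | 5.6% | 5.6% / 5.9% | 16.7% / 17.6% |
| 16 | 0.889 | 11.1% | 5.6% / 6.25% | 16.7% / 18.75% |
| 15 | 0.833 | 16.7% | 5.6% / 6.7% | 16.7% / 20.0% |
| 14 | 0.778 | 22.2% | 5.6% / 7.1% | 16.7% / 21.4% |

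The counts x = 1 and x = 3 are illustrations, not expectations from the documents. The same formula applies to the Itraconazole column, with m the number dosed from Day 8.

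**The mixed missing category**

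Take m = 14 with 3 abnormal, 10 normal and 1 recipient without an ECG (3 + 10 + 1 = 14). Under the current rule the column shows abnormal 3/18 = 16.7% and missing (4 + 1)/18 = 27.8%. On the recipient base it shows abnormal 3/14 = 21.4% and missing 1/14 = 7.1%. The current display cannot tell the four non-recipients from the one missed ECG.

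**The case against.** The strongest reply is that the rule hides nothing. Missing is a displayed category, the total is at most 18, and all ECG assessments are listed. A reader who sees 3 abnormal and 4 missing out of 18 can work out 3/14 at once. This largely stands. The remaining gap is that the rate among recipients, as opposed to those observed, also needs disposition data, because the missing category mixes the two groups.

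Second, the findings that matter most appear elsewhere on the right base. Protocol 7.1 requires a new clinically relevant finding to be reported as an AE, and AE tables divide by recipients. Protocol 9.4.2 also has noteworthy individual ECG findings listed and summarised. This stands, and it means that a reader who infers that the rule could conceal a clinically significant ECG signal goes further than the documents allow.

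Third, a reader might infer that the combination percentages will be about 22% too low. The documents do not support that. Fourteen is the planned minimum of evaluable completers, and evaluability is a PK concept in Protocol 9.3: a participant can receive the combination and later be non-evaluable or leave. The factor 0.778 needs all four allowed losses to fall before Day 12. With none before Day 12 there is no effect. Losses before that day are nonetheless possible; Protocol 7.2, for example, requires withdrawal for a positive SARS-CoV-2 test on admission on Day 11.

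Fourth, one might infer that every percentage outside the AE and PK tables is wrong, or that only the combination column suffers. Neither holds: the rule is a default that is harmless for overall tables, and the Itraconazole column is affected by losses before Day 8.

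**Conclusion.** The point holds in limited form. As written, SAP Section 9 puts participants who never received an intervention into that intervention's denominator in the ECG interpretation table. This is inconsistent with the SAP's own AE rule and with its as-treated principle. Each percentage in the combination column is m/18 of the rate among recipients, from no effect at m = 18 to 0.778 at m = 14, on the assumptions that 18 enter the Safety set and that losses fall before Day 12. For one or two such losses the factor is 0.944 or 0.889.

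The consequence is modest. It concerns one descriptive table of a secondary safety endpoint, can be seen from the table itself, and leaves the primary PK comparison, the AE tables and the continuous ECG summaries untouched. It is worth correcting because the stated base is wrong for the exposure being described and the correction is nearly free.

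**What to change.** In SAP Section 9, extend the AE/PK rule to every table presented by study intervention: the denominator is the participants of the analysis set who received that intervention. Keep [N] for overall tables such as demographics.

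Missing observations may stay in the denominator as a separate category, but counted among recipients only, so that the category means a recipient without an assessment. Removing missing from the percentages altogether is a matter of preference and is not needed to solve the problem.

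The cost is one sentence in a revised SAP and one changed denominator in the ECG interpretation table. No new data and no protocol change are required.
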